## **8.2 PRIOR AND CONCOMITANT MEDICATIONS**

Any prior medication received within 28 days of the first dose of study drug will be recorded in the case report form (CRF). All medications (or treatments) other than study drug taken or received by the subject at any time during the study from

screening through the 4-week follow-up visit will be considered concomitant medications (or treatments).

If a medication has an end date that occurs before first dose date, that medication will be considered a prior medication. If a medication has a start date that occurs before first dose date and an end date that occurs after first dose date, that medication will be considered both prior and concomitant. If a medication has a start date that occurs after first dose date, that medication will be considered concomitant. If a missing start date, start time, end date, or end time leads to ambiguity in whether a medication is prior or concomitant, the medication will be considered concomitant.

Prior and concomitant medications will be mapped to a World Health Organization Drug Dictionary Enhanced (WHO DDE), September 2015. The number and percent of subjects taking concomitant medications will be summarized by Anatomical Therapeutic Classification Level 1 code, by descending frequency at the PT level. Prior and concomitant medication will be listed.

### 8.3 CLINICAL LABORATORY PARAMETERS

Hematology, clinical chemistry, and urinalysis data will be collected at screening, the baseline/Day 1 visit, and at the Week 2, Week 4, Week 8, Week 12, Week 16, and Week 24 visits.

Coagulation profile will be performed only at screening, baseline, and Week 24 and will include INR.

Hematologic profile will report the following parameters: hematocrit, hemoglobin, mean corpuscular hemoglobin, mean corpuscular hemoglobin concentration, mean corpuscular volume, platelet count, red blood cell distribution width, red blood cell count, white blood cell count, and white blood cell differential (absolute counts only): basophils, eosinophils, lymphocytes, monocytes, and neutrophils.

Clinical chemistry profile will include: cholesterol (total), high-density lipoprotein, low-density lipoprotein, triglyceride, amylase (reflex lipase if amylase  $\geq 1.5 \times$  ULN), bicarbonate, blood urea nitrogen, calcium, chloride, creatine phosphokinase, creatinine, glucose, lactate dehydrogenase, magnesium, phosphorus, potassium, sodium, total protein, and uric acid.

Urinalysis profile will report color and appearance, pH and specific gravity, bilirubin, glucose, ketones, leukocytes, nitrite, occult blood, protein, and urobilinogen.

All hematology, coagulation, clinical chemistry, and nominal urinalysis data will be summarized at each time point for the actual values and for changes from baseline. Descriptive summaries of quantitative changes in urinalysis will be presented by study visit in a separate table.

Laboratory abnormalities will be graded according to NCI CTCAE, Version 4.03, and recorded as AEs.

The number and percentage of subjects experiencing with Grade 3 or 4 Treatment-emergent abnormal clinical chemistry values will be presented.

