### ***11.4.2 Laboratory Assessments***

#### 11.4.2.1 Measurement of Laboratory Assessments

A central laboratory will perform all clinical safety laboratory tests. Urine drug screens will also be analyzed at the central laboratory. Urine pregnancy tests will be performed at the site using a dipstick method, except at Screening where a serum pregnancy test will be performed. If there is a positive urine pregnancy test while on-study, a serum pregnancy test will be conducted by the central lab.

Samples for hematology, serum chemistry, liver function tests and urinalysis will be prepared using standard procedures. Refer to the laboratory manual provided by Tobira for further details and specifications for sample handling, processing, and shipment.

A complete list of all laboratory tests is provided in Appendix [20.5](#).

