#### 11.4.6.4 Management of Subjects with Elevated ALP, ALT, AST or Bilirubin

If a subject is *asymptomatic* but experiences clinically significant elevations of liver transaminases or Bilirubin, subjects must repeat physical examination and laboratory evaluation within 48-72 hours for repeat testing and close monitoring, preferably at the clinical research site or alternately at a local laboratory.

[REDACTED]

- 1 [REDACTED]

- 2 [REDACTED]

- 3 [REDACTED]

For confirmed elevations of above parameters, the subject must interrupt study drug. Close monitoring of study subjects includes:

- 1 [REDACTED]

- 2 [REDACTED]

- 3 [REDACTED]

- 4 [REDACTED]

- 5 [REDACTED]

- 6 [REDACTED]

- 7 [REDACTED]

[REDACTED]

[REDACTED]

[REDACTED]

[REDACTED]

- 1 [REDACTED]

[REDACTED]

- [REDACTED]
- [REDACTED]
- [REDACTED]

[REDACTED]

[REDACTED]

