### **12.5.2.2 Clinical Laboratory Tests**

Descriptive summaries of clinical laboratory results will be presented by study visit. Laboratory abnormalities will be graded according to NCI CTCAE version 4.03 (see Appendix [20.2](#)). The number and percentage of subjects experiencing treatment-emergent graded toxicities will be summarized by treatment group and severity grade. Laboratory toxicity shifts from Baseline to post-Baseline assessments will be summarized by treatment group. Changes from Baseline in laboratory tests will be summarized for each treatment group.

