## 1.7 SCOPE OF PLAN

This statistical analysis plan (SAP) provides a more technical and detailed elaboration of the statistical analyses of the efficacy and safety data as outlined or specified in the final protocol of Study Protocol 652-205 (version dated 19 November 2015) and the most recent amendment (Version 3 dated [14 June 2016]). Specifications of tables, figures, and data listings are contained in a separate document.

This SAP will indicate the methods to be used to analyze the safety and efficacy data collected during the study and will supersede any statistical analyses specified in the protocol. The planned analyses identified in this SAP will be included in regulatory submissions and future manuscripts. Additional exploratory analyses, which are not defined in this SAP, will be labeled as such in any study report or regulatory submission.

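### SAP 8.3 narrows the protocol's graded laboratory safety analysis to Grade 3/4 clinical chemistry and drops the baseline shift tables, without declaring the change

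*SAP*

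**What the plan says.** Protocol 12.5.2.2 sets two graded laboratory outputs. One is a count: "The number and percentage of subjects experiencing treatment-emergent graded toxicities will be summarized by treatment group and severity grade". The other is movement between grades: "Laboratory toxicity shifts from Baseline to post-Baseline assessments will be summarized by treatment group". Neither is confined to a particular panel. The section also plans descriptive summaries by visit and changes from Baseline.

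SAP 8.3 keeps the visit summaries of values and changes for hematology, coagulation, chemistry and urinalysis. Its only count by laboratory grade is this: "The number and percentage of subjects experiencing with Grade 3 or 4 Treatment-emergent abnormal clinical chemistry values will be presented". The same section spells out the panel. It opens "Clinical chemistry profile will include: cholesterol (total), high-density lipoprotein, low-density lipoprotein, triglyceride, amylase" and closes "lactate dehydrogenase, magnesium, phosphorus, potassium, sodium, total protein, and uric acid". SAP 1.7 states that the SAP "will supersede any statistical analyses specified in the protocol".

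Two further statements bear on the point. SAP 8.3 says that laboratory abnormalities are graded by CTCAE and entered as adverse events. Protocol 11.4.1.1.6 requires an adverse event only when a repeat test confirms the abnormality and the investigator judges that the change from Baseline calls for a change in management.

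**The concern.** Safety and tolerability is the only secondary objective stated in either document. Every subject enters with ALP of at least 1.5 × ULN. AST up to 200 IU/L is allowed at Screening, as is ALT up to 250 IU/L in men and 200 IU/L in women. When subjects start out abnormal, the informative safety question is how many moved to a worse grade than they had at entry. A shift table answers that; a count of Grade 3 or 4 chemistry values does not.

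Because the SAP takes precedence, protocol 12.5.2.2 is not a fallback. A programmer who follows SAP 8.3 will produce neither the all-grade count nor the shifts. SAP 2.1.2 openly says that the planned per-protocol analysis has been dropped, but the visible text says nothing comparable here. The report could therefore answer the secondary objective with less than the protocol promised, and its reader would not know.

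**Working it through.** No sample size, power or event figure is involved, so the check is a comparison of texts.

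**Step 1. Planned outputs side by side.**

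| Output | Protocol 12.5.2.2 | SAP 8.3, as visible |
|---|---|---|
| Grades counted | Every severity grade | Grades 3 and 4 |
| Tests counted by grade | Laboratory tests generally | Clinical chemistry |
| Hematology and coagulation by grade | Within scope | None |
| Grade shifts from Baseline | Planned | None |
| Values and changes from Baseline | Planned | Kept |

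The SAP has not rejected shift tables in general, since SAP 8.4 plans one for the ECG interpretation.

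**Step 2. Does the counted panel contain liver tests?** The SAP 8.3 chemistry list has 19 analytes, plus a reflex lipase. A search of that list for ALT, AST, ALP, bilirubin, GGT, albumin and bile acids gives 0 matches. Bilirubin appears in 8.3 only as a urinalysis item, and 8.3 has no separate liver panel. The protocol names liver tests apart from chemistry, both in the synopsis list of procedures and in 11.4.2.1: "Samples for hematology, serum chemistry, liver function tests and urinalysis will be prepared using standard procedures". Read literally, the graded count leaves liver tests out.

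**Step 3. Does the adverse-event route fill the gap?** A graded laboratory value reaches the tables of treatment-emergent adverse events by grade (SAP 8.1.1) only if a site recorded it as an adverse event. On the wording of SAP 8.3, that happens for laboratory abnormalities without further condition. Under protocol 11.4.1.1.6 it is required only after confirmation and a judgment of clinical significance. Sites record under the protocol, and an SAP sentence cannot create entries that they did not make. Protocol 11.4.1.1.5 adds uncertainty for liver tests: it covers worsening of illnesses other than the disease under study and gives no matching instruction for PSC. The endpoint kept in SAP 8.0, the proportion with a clinically significant laboratory abnormality, depends on the same judgment, and visible 8.3 specifies no table for it.

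**Step 4. Do the visit summaries fill the gap?** SAP 3.1 gives minimum, maximum, quartiles and the 10th and 90th percentiles. These describe one visit at a time. They do not give each subject's worst grade over follow-up, nor that grade cross-classified by baseline grade. Visible 8.3 also does not say how unscheduled results enter.

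**The case against.** The case on the other side is substantial. The sentence in SAP 8.3 just before the quoted count sends graded abnormalities to the adverse-event tables with no limit on panel or grade. Those tables have a row for each observed grade, and the SAP definition of treatment-emergent includes an existing event that worsens in grade. Visit summaries with extremes and percentiles remain, and with about 25 subjects a large change would be visible there and in the listings. ALP is the primary endpoint and is summarized at each visit, and the subject profiles in SAP 7.4 plot it with ALT. The panel is introduced by a verb that may not be exhaustive, and protocol 11.4.2.1 is about sample handling rather than analysis. Table specifications sit in a separate document.

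All of this stands as a limit on the point. None of it restores the protocol's laboratory-based grade counts or shift tables.

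Three stronger readings are tempting and not supported:

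- A reader might infer that liver toxicity goes uncounted. The adverse-event tables are open to liver terms, and SAP 8.1.2 and much of the text after SAP 7.2 are redacted and may hold a liver analysis.
- A reader might infer that local repeat tests are lost, since protocol 11.4.6.4 allows repeats "preferably at the clinical research site or alternately at a local laboratory" while protocol 15.1 describes central laboratory datasets. No text excludes local results, and protocol 15.2.1 has the CRF take all protocol-specified data. The loss is possible but not shown.
- A reader might expect the SAP 8.3 table to show a misleading zero for lower-grade or hematology events. It would have no row for them, so no zero would appear.

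**Conclusion.** The concern holds in a limited form. SAP 8.3, as visible, reduces the protocol's graded laboratory analysis in four respects: grades are cut to 3 and 4, tests are cut to chemistry, hematology and coagulation lose any laboratory-based graded count, and the shift tables go. The change is not declared. The chemistry list contains no liver test, but what the SAP as a whole does with liver tests cannot be judged from the visible text.

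The size is a loss of planned output on the only secondary objective. The documents give no rates of laboratory abnormality, so the number of subjects affected cannot be estimated. The primary ALP analysis is untouched.

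The conclusion assumes that SAP 8.3, which shows no redaction, is complete as printed; that the separate table specifications do not restore the protocol outputs; and that the SAP governs, as SAP 1.7 says. The loss of shifts, lower grades and graded hematology and coagulation in 8.3 does not depend on how the redacted liver text reads.

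**What to change.** In SAP 8.3:

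1. Restore both protocol 12.5.2.2 outputs: the number and percentage of subjects by maximum treatment-emergent CTCAE grade, and shift tables from baseline grade to worst post-baseline grade.
2. Compute both from laboratory values, using all post-baseline results including unscheduled ones, and define treatment-emergent for a laboratory grade (for example, a grade above the baseline grade).
3. Apply them to hematology, coagulation, chemistry and an explicitly named liver panel (ALT, AST, bilirubin, ALP, GGT and albumin). If another SAP section already gives these outputs for liver tests, cross-refer to it.
4. Reconcile the SAP 8.3 statement on recording laboratory abnormalities as adverse events with protocol 11.4.1.1.6.

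If the sponsor prefers the narrower output, the SAP should declare and justify the departure, as SAP 2.1.2 declares its own. The cost is SAP wording and a few standard tables.

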#### **8.4 ELECTROCARDIOGRAMS**

A 12-lead ECG will be taken at the baseline/Day 1 visit, and at Week 24. ECGs will be performed with the subject in the supine position after 5 minutes of rest and before any blood draws. ECG parameters include ventricular heart rate (beats/min), RR interval (msec), PR interval (msec), QRS interval (msec), QT interval (msec), QTcF interval (msec). Results will be classified as follows: normal; abnormal, not clinically significant; and abnormal, clinically significant.

Descriptive statistics for ECG parameters (heart rate, RR interval, PR interval, QRS duration, QT interval, and QTc) at each visit (Baseline and Week 24) and changes from baseline values at Week 24 will be presented. The QTc will be calculated using the Fridericia correction.

A shift table from baseline to Week 24 in the clinical significance as per investigator's overall interpretation of the ECG will be presented for the following categories: normal; abnormal, not clinically significant; and abnormal, clinically significant. The tabular display will also show total number of subjects with post baseline, clinically significant ECG abnormalities according to the investigator's overall interpretation.

ECG data will be listed.

## **8.5 VITAL SIGNS**

Vital sign measurements (sitting systolic and diastolic blood pressure, temperature, heart rate, and respiration rate) will be taken at screening, the baseline/Day 1 visit, and at the Week 2, Week 4, Week 8, Week 12, Week 16, and Week 24 visits.

Descriptive summaries of raw values of vital signs (systolic blood pressure, diastolic blood pressure, heart rate) will be presented at study visit. Descriptive summaries of changes from baseline in vital signs will also be presented by study visit.

Vital signs will be listed.

## **8.6 PHYSICAL EXAMINATION**

A complete physical examination will be performed at the Screening 1 visit and the baseline/Day 1 visit. A symptom-directed physical examination will be performed, as needed, at the Screening 2 visit, at all on-treatment visits, at the early discontinuation visit within 48 hours of stopping study medication, and at the 4-week follow-up visit. The complete physical examination will include (but will not be limited to) the following organ or body system assessments: skin; head, eyes, ears, nose, and throat; thyroid; lungs; cardiovascular; abdomen (liver and spleen); extremities; lymph nodes; and a brief neurological examination. Abbreviated symptom-directed physical examinations will target signs and symptoms.

Any abnormal findings that are considered clinically significant in the opinion of the investigator will be recorded as AEs or be captured as medical history, if already present at screening.

Physical examination data will be listed.

## **8.7 PROCEDURES AND THERAPIES**

Any procedures and non-drug therapies administered during the study that are recorded in the (CRF) will be listed.

## 9.0 SPECIFICATIONS FOR ANALYSIS DISPLAYS

### 9.1 ANALYSIS DISPLAY FORMAT

All analysis displays will be created by using statistical and summarization procedures in [REDACTED]. Displays will be produced by using the Courier New 8-point font. Headers will also be in Courier New 8-point font.

All displays are intended to be printed as landscape on 8.5- × 11-in paper. The top and bottom margins will be 0.50 in, and the left and right margins will be 0.75 in.

### 9.2 CONVENTIONS FOR PRESENTATION

The conventions for presentation in the analysis displays are shown in Table 2.

**Table 2 Conventions for Presentation in the analysis displays**

Convention	Description
Decimals for summary statistics	General rule: Relative to number of decimals in original data, use 1 more decimal for mean, median, and percentiles, 2 more decimals for standard deviation/error, and same number for minimum, maximum, and range. Do not exceed 4 decimals. Some laboratory parameters or other data may require judicious deviation from this rule.
Format for percentages	Display percentages with 1 decimal.
Sort order in listings	Subject identification is sorted sequentially.

### 9.3 CONVENTIONS FOR CALCULATIONS AND TABULATIONS

The conventions for calculations and tabulations are shown in Table 3.

**Table 3. Conventions for Calculations and Tabulations**

Convention	Description
Age calculation	Age is calculated as an integer in years as the difference between the subject's date of informed consent and the date of birth.
AE counting: general summary	In summary displays, AEs are counted only once per subject within MedDRA category (e.g., overall, system organ class, and preferred term).
AE counting: summary by assessment	When AEs are summarized within levels of another AE assessment (e.g., causality or severity), AEs are counted once per subject at the worst level of the assessment (e.g., strongest relationship to study drug or greatest severity). A missing or unknown value for the assessment will be considered Unknown.
"Other" category counting	For purposes of summarization, conditions recorded in the case report form as an "Other" category condition will be counted only once per subject. Hence, the count becomes the number of subjects reporting at least one "Other" condition vs. subjects reporting none. All conditions will be listed in the appendix.

AE = adverse event; MedDRA = Medical Dictionary for Regulatory Activities.

